### **5.8 End of Study**

The End of Study eCRF is required to be completed whenever a patient exits the study. This includes patients enrolled in the study who:

- Complete the study protocol, after 12 months of follow up
- Voluntarily withdraw from the study
- Withdrawn by the study Investigator
- Met the definition of endoAVF abandonment (see Section 4.3)
- Lost to follow-up
- Deceased
- Other reason(s) for exiting the study

## 6 ADVERSE EVENTS

An Adverse event (AE) will be defined as any adverse medical change (i.e., *de novo* or increased severity in a preexisting condition) from the patient's baseline condition that occurs during the course of the clinical study, after starting treatment, whether considered treatment-related or not. "Treatment" includes all commercially-approved products administered according to the study protocol and specific Instruction for use (IFU) documents.

Any pre-planned procedures (refer to Section 4.5.3- 2nd-Stage Procedures), or additional interventions, will not be considered AEs for this study. In addition, normally expected symptoms caused by the treatment that do not prolong or affect patient discharge, or are managed with observation alone and do not require intervention (e.g., medical, endovascular, surgical) are not considered an AE for this study.

These may include but are not limited to:

- Transient arterial spasm resolving spontaneously OR with medication only
- Minor discomfort or bruise at the arterial access site
- Small amount of bleeding at point of arterial access
- Transient numbness, tingling or coolness that resolved within 4 weeks post index procedure
- Bruising at the AVF creation site
- Side effects of standard-of-care medications
- Hematoma at the arterial and/or venous access site(s) and did not require endovascular or surgical intervention nor adversely affected discharge.

Only AEs that are relevant to index procedure, study device, access site or the endoAVF will be collected in the study. For example, if the subject has knee replacement or undergoes a hysterectomy, these events will be considered as non-study related and will not be required to be recorded via Adverse Event eCRF.

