**Number of Patients Who Met Functional Cannulation:** Functional Cannulation is defined as 2-needle access of the endoAVF access circuit with performance of  $\geq 2/3$ rds of  $\geq 120$  minute dialysis sessions through the endoAVF access circuit over a continuous 28-day period.

**Central Venous Catheter (CVC) Exposure:** CVC exposure will be analyzed at the follow-up time points, presenting the number/percent of patients reporting CVC use and the number/percent reporting dialysis access through other means, as well as the number/percent of subjects not yet on dialysis.

**Adverse Events:** Rate of serious procedure or device related Adverse Events (AEs) throughout the study period. The relevant events and rates of occurrence will be analyzed with a time component, to analyze procedural AEs and post-procedural AEs.

**Intervention Rate:** The percentage of patients requiring intervention will be calculated at 3, 6 and 12 months follow-up visits post index procedure. The rate of interventions that occurred during the index procedure and during short term follow-up will also be calculated.

The endoAVF-related interventions include:

- Interventions to maintain or restore patency of the endoAVF, including endovascular and surgical procedures designed to address occlusive thrombosis (resulting in absence of thrill or bruit at endoAVF) and clinically significant occlusive stenosis at or near endoAVF site.
- Interventions to support maturation of the arterialized vein segments, including endovascular procedures such as secondary coil embolization to facilitate flow into the target cannulation veins.
- Interventions to support cannulation of the arterialized vein segments, including procedures such as a superficialization or elevation where the target cannulation vein is brought closer to the skin surface to enable cannulation, without the creation of a new AV fistula.
- Any intervention to address any complications or adverse events of the access circuit.

**Note:** Any additional procedure performed at the time of the index procedure to address an adverse event will require a Post-Procedure Intervention eCRF to be completed.

**Note:** Diagnostic fistulogram, angiogram or duplex ultrasound will not be considered an intervention for the purpose of this study.

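### The Section 6 rule for what is not an adverse event can be read two ways and conflicts with its own examples, so some treated symptoms could go uncounted

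*Combined protocol and SAP*

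**What the plan says.** Section 6 takes a class of events out of the AE definition. The class is "normally expected symptoms caused by the treatment", provided that they "do not prolong or affect patient discharge, or are managed with observation alone and do not require intervention (e.g., medical, endovascular, surgical"). An open list of examples follows. Four matter here:

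- "Transient arterial spasm resolving spontaneously OR with medication only"
- "Transient numbness, tingling or coolness that resolved within 4 weeks post index procedure"
- "Hematoma at the arterial and/or venous access site(s) and did not require endovascular or surgical intervention nor adversely affected discharge"
- "Side effects of standard-of-care medications"

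Table 6-1 defines a serious adverse event (SAE) as an AE with certain consequences. Section 6.1 sends reported AEs to the independent Clinical Events Committee (CEC). The safety outcome in Section 4.3 is the "Rate of serious procedure or device related Adverse Events (AEs) throughout the study period", with procedural and post-procedural events analysed separately. Section 7 states that the study is observational and tests no hypotheses.

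**The concern.** The two limbs of the exclusion are joined by 'or'. Read in the ordinary way, a symptom need only leave discharge unaffected to be excluded, whatever treatment it needs. A symptom that begins after the patient has gone home cannot delay that discharge, so it would pass the first limb automatically. The sentence can also be read so that the closing words on intervention govern both limbs, and then the same symptom is an AE.

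Up to 20 sites would apply this definition. If they read it differently, the AE counts depend partly on the site's reading. Where the permissive reading is used, treated symptoms drop out before any form is completed or any adjudication takes place. In a descriptive study the reported rates are the product, and Section 4.2 says the data may support reimbursement and publications.

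**Working it through.** **Inputs.** From Section 6: A = the symptom does not affect discharge; B = it is managed by observation alone; C = it needs no intervention, where medical, endovascular and surgical treatment are named as interventions. From Section 4.1: up to 200 treated patients. The plan gives no expected AE rate and no sample-size derivation, so it has no figure to reproduce.

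**Step 1: what each reading does.** Entries say whether an expected symptom is an AE. Combinations with B true and C false are left out, because observation alone implies no intervention.

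| A | B | C | Ordinary: A or (B and C) | Second: (A or B) and C | Both conditions: A and B and C |
|---|---|---|---|---|---|
| yes | yes | yes | not an AE | not an AE | not an AE |
| yes | no | yes | not an AE | not an AE | AE |
| yes | no | no | **not an AE** | **AE** | **AE** |
| no | yes | yes | not an AE | not an AE | AE |
| no | no | yes | AE | AE | AE |
| no | no | no | AE | AE | AE |

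The two available readings differ in one row only: the symptom needs intervention but does not affect discharge.

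**Step 2: whether the examples choose between the readings.**

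| Example | Treatment condition | Discharge condition | Agreement with the rule |
|---|---|---|---|
| Arterial spasm | medication allowed | none | fits the ordinary reading if discharge is unaffected; contradicts the second, since medical treatment is a named intervention |
| Numbness, tingling, coolness | none; must be transient and gone within 4 weeks | none | states neither condition |
| Access-site hematoma | no endovascular or surgical intervention; medical not mentioned | must not be adversely affected | needs both conditions, so stricter than the ordinary reading; looser than the second on medical treatment |
| Medication side effects | none | none | states neither condition |

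No single reading of the rule reproduces all four.

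**Step 3: whether a later step recovers an excluded event.** Under Section 5.5, an unscheduled visit with no AE noted needs no form, apart from the intervention form for patency, maturation or cannulation procedures. Under Table 6-1, an event that is not an AE cannot become an SAE. Under Section 6.1, the CEC sees reported AEs only. So nothing restores the event to the Section 4.3 safety outcome.

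To be lost from the *serious related* rate, an event must meet four conditions at once: it counts as normally expected, it leaves the index discharge unaffected, it meets a full Table 6-1 seriousness criterion, and it is related to the device or procedure. An expected symptom that starts at home and leads to a later hospital admission is one such path.

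**Step 4: size.** With T patients who truly have a serious related event, m of them missed and n = 200, the reported rate is (T − m)/200. Each missed patient changes it by 1/200 = 0.5 percentage points. T and m are assumptions.

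| T (true rate) | m = 0 | m = 1 | m = 2 | m = 4 |
|---|---|---|---|---|
| 4 (2.0%) | 2.0% | 1.5% | 1.0% | 0.0% |
| 10 (5.0%) | 5.0% | 4.5% | 4.0% | 3.0% |
| 20 (10.0%) | 10.0% | 9.5% | 9.0% | 8.0% |

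For scale, the exact 95% interval at 10/200 is 2.4% to 9.0%, and at 6/200 it is 1.1% to 6.4%.

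**The case against.** The strongest reply is that the gap is narrow and may be empty.

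- The second reading is a fair one, and it closes the gap. The hematoma example, which demands that discharge be unaffected *and* that no endovascular or surgical step be needed ("did not require endovascular or surgical intervention nor adversely affected discharge"), is evidence against treating either limb as sufficient. This stands: the defect is ambiguity, not a settled permissive rule.
- The exclusion reaches only normally expected symptoms. Section 3.2 lists steal syndrome or ischemia separately from numbness, tingling and coolness, and nothing in Section 6 excludes ischemia by name. This stands, although 'normally expected' is not defined and the list is open.
- A reader might infer that Table 6-1 makes any treated event serious. It does not. The intervention criterion applies to a serious deterioration in health where treatment was given to avert a threat to life or lasting impairment. Most symptoms that this rule removes would therefore be non-serious and outside the serious related rate in any case.
- An event that prolongs the index stay fails the discharge limb, so that limb does not exclude it.
- Section 4.3 counts interventions for access-circuit complications in the intervention rate, so an access revision would still be reported there. That is partial cover only: the intervention rate is a separate outcome, without the seriousness, relatedness and CEC review that apply to AEs.

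What the reply does not remove is the conflict between the rule and its examples, or the narrow path in Step 3.

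**Conclusion.** The point holds as one of ambiguous and internally inconsistent wording. On the ordinary reading, a treated expected symptom that leaves discharge unaffected is not an AE; on the other reading it is; and the examples do not decide between them. The wording *could* understate the AE rate and, by the narrower path, the serious related AE rate. Any such error can only be downward.

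A reader might go further and conclude that the serious related rate *is* understated, or take a figure such as 20% to 40% from the T = 10 row (2 or 4 of 10 missed). The documents do not support either conclusion. They give no event counts and do not show how sites read the rule, and the number missed may be zero. The firm figure is 0.5 percentage points per missed patient with 200 patients in the denominator, and more if fewer are enrolled. No hypothesis test or sample-size figure is affected.

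**What to change.** Amend Section 6 as follows.

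1. In the exclusion sentence, change the 'or' after the comma, which introduces management by observation alone, to 'and'. An expected symptom is then excluded only if it leaves discharge unaffected, is managed by observation alone and needs no intervention.
2. State that this rule governs every listed example, including medication side effects.
3. State that any event meeting a Table 6-1 seriousness criterion is an AE, whatever the list says.
4. Reconcile three examples with the rule: spasm (medication allowed, though medical treatment is a named intervention), numbness, tingling or coolness (no condition on how it resolved), and hematoma (medical treatment not mentioned).

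The cost is a wording amendment and a memo to sites, a few more AE forms and CEC reviews, and possibly a slightly less favourable AE rate. Expected symptoms that were only observed but did affect discharge would also become AEs, which agrees with the discharge condition already in the hematoma example.

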**Table 6-1: Adverse Event Type**

AE Type	Definition
Serious Adverse Event (SAE)	AE that: 

• led to death,

• led to serious deterioration in the health of the patient, that either resulted in:

◦ a life-threatening illness or injury, or

◦ a permanent impairment of a body structure or a body function, or

◦ in-patient or prolonged hospitalization, or

◦ medical or surgical intervention to prevent life-threatening illness or injury or permanent impairment to a body structure or a body function,

• led to fetal distress, fetal death or a congenital abnormality or birth defect

Adverse Device Effect (ADE)	AE related to the use of study device.  NOTE: This definition includes adverse events resulting from insufficient or inadequate IFU, deployment, installation, operation, or any malfunction of the study device. In addition to any event resulting from use error or from intentional misuse of the study device.

Serious ADE (SADE)	ADE that has resulted in any of the consequences characteristic of a SAE.
Unanticipated SADE (USADE)	USADE which by its nature, incidence, severity or outcome has not been identified in the current version of the study protocol, IFU, or other study documentation.

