## **6.1 Relationship to Device or Procedure**

The Investigator will also evaluate the relationship of the adverse event to the everlinQ endoAVF System or procedure according to the following definitions:

**Definite (YES):** The AE follows a reasonable timing from treatment (or attempted treatment) with the device and the possibilities of factors other than the device or the index procedure, such as underlying disease, concomitant drugs, or concurrent treatment can be excluded. This includes an AE that occurs during the index (endoAVF creation) procedure.

**Probable (YES):** The AE follows a reasonable timing from treatment (or attempted treatment) with the device and the probability of device or procedure involvement cannot be excluded. However, other factors such as underlying disease, concomitant medications, or concurrent treatment may be possible.

**Unlikely (NO):** The AE follows an unlikely timing relationship from treatment (or attempted treatment) or is more likely due to other factors and there is no definitive information suggesting that it was related to the device or procedure.

**Not Related (NO):** The AE has no timing relationship from treatment (or attempted treatment) or it can be explained by other factors, including underlying disease, concomitant medication, or concurrent treatment.

The Investigator will evaluate the relationship to the everlinQ device portion of the procedure using the yes/no definitions above. The everlinQ device portion of the procedure only includes insertion, deployment and removal of the everlinQ catheters.

All reported adverse events will be reviewed and adjudicated by an independent Clinical Events Committee (CEC).

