**Table 8-1: Investigator Reports**

Report	Submitted To	Description
Unanticipated Serious Adverse Device Events and Serious Adverse Device Effects	Sponsor & EC	The Investigator's report on any unanticipated serious adverse device event (USADE) or serious adverse device effect (SADE) must be submitted within 10 working days after the Investigator first learns of the event.
Deviations from study protocol		All deviations must be documented on a Protocol Deviation Form.
Serious Adverse Events	Sponsor	The Investigator's report on any Serious Adverse Events (SAEs) must be submitted within 10 working days after the Investigator first learns of the event
Withdrawal of EC approval		The Investigator must report a withdrawal of reviewing EC approval within 5 working days.

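### Section 6 and Table 8-1 give different rules for serious adverse events, and nothing ensures that those left off the AE form reach the Clinical Events Committee

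*Combined protocol and SAP*

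**What the plan says.** The relevant statements are spread over several sections of the protocol.

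- **Section 6, definition.** An AE is an adverse medical change "that occurs during the course of the clinical study, after starting treatment, whether considered treatment-related or not".
- **Section 6, collection rule.** "Only AEs that are relevant to index procedure, study device, access site or the endoAVF will be collected in the study". The examples of what falls outside are a knee replacement and a hysterectomy: "these events will be considered as non-study related and will not be required to be recorded via Adverse Event eCRF". No exception is made for serious events.
- **Table 6-1.** An SAE is defined by its consequences alone, and these include "in-patient or prolonged hospitalization". Relatedness is not a condition.
- **Table 8-1.** The investigator's "report on any Serious Adverse Events (SAEs) must be submitted within 10 working days after the Investigator first learns of the event". The recipient is the sponsor. This row is separate from the row for serious and unanticipated serious device effects.
- **Section 6.1.** The investigator rates relationship to device and procedure, and then: "All reported adverse events will be reviewed and adjudicated by an independent Clinical Events Committee (CEC").
- **Section 4.3.** The adverse-event outcome is the rate of serious events related to the procedure or the device over the study period.
- **Section 8.10.** When listing source documents to be requested, the sponsor names SAEs separately from related AEs.
- **Section 5.8.** Death is a reason for completing the End of Study eCRF.

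**The concern.** The safety outcome counts serious events that are called related, and the protocol sets up an independent committee to adjudicate events. That protection works only for events the committee receives. A relevance filter applied before an event is recorded decides part of the question in advance. The committee can reclassify an event in either direction once it has it, but it cannot reclassify one that was never sent.

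The events at risk are serious ones with more than one plausible cause. Section 3.2 lists death as a potential risk and describes it as mostly due to kidney disease, and it describes arrhythmia in similar terms. That wording could lead a site to set such an event aside as not relevant. Independent review is most useful for exactly these cases. Section 4.2 says the data may support reimbursement and publications, so readers outside the study may rely on the reported rate.

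**Working it through.** The plan gives no figure for an expected SAE rate, so there is nothing to reproduce. The check is a side-by-side reading, followed by one line of arithmetic on scale.

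**Step 1: is there a conflict for serious events?** Take one of Section 6's own examples. A knee replacement normally involves a hospital stay, which Table 6-1 counts as a serious consequence. If it arises as an adverse change during the study, Table 8-1 asks for a report to the sponsor, while Section 6 says it is not collected on the AE eCRF. The same event is therefore reportable under one rule and outside collection under the other. Section 8.10 leans towards Table 8-1, because it expects SAE documents apart from related AEs.

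**Step 2: what does the committee receive?** Section 6.1 sends it reported events. Section 8.3 adds only that it reviews and adjudicates adverse events. Neither says whether an SAE report under Table 8-1 without an AE eCRF is a reported event in this sense. Nothing gives the committee a list of uncollected events, and nobody independent checks the relevance decision. A death appears on the End of Study eCRF, but Section 5.8 does not route it to the committee.

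**Step 3: consequences under each reading.**

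| Reading | SAEs the committee sees | Effect on the related-SAE rate |
|---|---|---|
| Table 8-1 governs and its reports count as reported events | All | No loss from the filter |
| Section 6 governs | Only those judged relevant | Understated by any omitted event the committee would have called related |
| Both are followed, with SAE reports kept outside the AE eCRF | Unclear; possibly only those judged relevant | As in the row above if not forwarded |

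**Step 4: scale.** Let N be the number of patients and O the number missing from the numerator because their only related SAE was omitted. For a per-patient rate, the understatement is O / N. At the cap of N = 200, one patient is 1 / 200 = 0.5 percentage points.

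To show how far this could run, two inputs must be assumed, and neither is in the documents: the share of patients with an SAE left off as not relevant (5% to 20%), and the share of those the committee would call related (5% to 20%).

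- Low end: 200 × 0.05 = 10 patients; 10 × 0.05 = 0.5 patients; 0.5 / 200 = 0.25 percentage points.
- High end: 200 × 0.20 = 40 patients; 40 × 0.20 = 8 patients; 8 / 200 = 4.0 percentage points.

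The sixteen-fold spread comes entirely from the assumptions. It illustrates the mechanism and does not estimate its size.

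**The case against.** The strongest reply is that the affected outcome concerns serious events only, and for those the protocol may already do what is wanted. Table 8-1 calls for every SAE, Section 8.10 expects SAE documents, and Section 6.1 sends all reported events to the committee. Read together, these could bring every SAE to adjudication. This stands as a possible reading, so the loss is conditional. It does not remove the point, because Section 6 has no exception for SAEs and no section makes the link from the SAE report to the committee.

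Several stronger readings are tempting and are not supported:

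- A reader might infer that the broad AE definition contradicts the narrow collection rule. It does not. Defining events widely and collecting a subset is ordinary scope-setting, and targeted collection is defensible in an observational post-market study with no hypothesis tests. The conflict is between the collection rule and the SAE row of Table 8-1.
- A reader might infer that only events the site already thinks related reach the committee. The filter is wider than that: it also admits events relevant to the access site or the fistula, and Section 6.1 keeps categories for unlikely and unrelated events. The committee can therefore upgrade some of what it receives. Section 6 does, however, justify non-recording on the ground that such events are not study related.
- A reader might infer that the rate can only be too low. That holds for omission alone. Section 6.1 classes as related any event during the index procedure, and also events for which device involvement remains possible alongside other causes, so upward error is possible too.
- Section 6 does not name who judges relevance. That it is the site is an inference, though a strong one: the investigator files the reports and rates relationship, and no other role is described as screening events first.
- Not every risk in Section 3.2 invites omission. Heart failure is tied there to fistula flow, and infection is listed with no attribution to kidney disease, so a site has reason in the text to treat both as relevant.

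**Conclusion.** The point holds in conditional form. Section 6 can exclude a serious event from collection, Table 8-1 requires the same event to be reported, and the protocol does not say which rule decides what the committee adjudicates. If Section 6 governs, serious events and deaths judged not relevant go unadjudicated, and the rate of related serious events can be understated through that omission. If Table 8-1 governs and its reports are forwarded, this loss does not occur.

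The size cannot be derived from the documents. The 0.5 points per omitted patient assumes that the cap of 200 is reached and that the rate is counted per patient. The range of 0.25 to 4.0 points rests in addition on two assumed proportions, and the conclusion does not depend on it. The matter deserves correction because a stated rule, on one natural reading, can remove events from the only adverse-event outcome that Section 4.3 defines before independent review takes place.

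**What to change.** Reconcile Sections 6 and 6.1 with Table 8-1:

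1. In Section 6, limit the relevance filter to non-serious AEs.
2. State that every SAE and every death reported under Table 8-1 is entered on the AE eCRF, whatever the site's view of its relevance.
3. In Section 6.1, state that the CEC adjudicates all of these for relationship to the device and the procedure.

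The cost is a protocol wording change, more SAE forms from sites, and more review in a population where serious illness unconnected with the access can be expected. Table 8-1 already requires the SAE reports and the committee already exists, so no new reporting duty or body is needed.

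If the sponsor prefers to keep the filter for serious events, the protocol should say so and Table 8-1 should be aligned with it. The rate should then be described, wherever it is reported, as conditional on site-judged relevance. This costs less, but it leaves the possible omission in place.
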